1. To examine the preliminary outcomes and acceptability of a multicomponent online commercial weight loss program that includes a mobile app, weekly virtual workshops, and an online community. Preliminary outcome is defined as weight change from baseline to 3 and 6-months. Secondary preliminary outcomes include changes in diet quality, physical activity, quality of life, sleep quality, and food cravings from baseline to 6 months. Acceptability of each program component and the overall program will be evaluated at 6 months.
2. To examine whether greater app use, greater engagement in the online community, and engagement with a higher number of peers (in the online community) predict greater weight loss at 3- and 6-months.
3. To examine the associations between total use of program components (and each individual program component) and change in weight. We hypothesize that greater use of program components (individually and total) will predict greater weight loss.

For EACH Participant Population State the Number of Participants to be Enrolled and Screened and/or the number of participant records reviewed (including, HIPAA covered health records and FERPA covered school records), if applicable: [State the total number of participants/records to be enrolled and, if enrolling more than one participant population, describe the total enrollment for each. Tip: consider attrition and the number of participants who may fail screening. Use of a range may provide flexibility. Note that the range must be justified in the **Justification of Sample Size section below.**]

The total number of subjects that will be enrolled into the intervention will be 150. It is estimated that we will screen 2,000 participants to achieve this recruitment goal. Since the initial contact is via an online link, there will be many incomplete responses driving up the number of screened-out participants.

Justification of Sample Size: [For qualitative and pilot studies, describe how the proposed sample size is appropriate for achieving the anticipated results. For quantitative studies, provide a power analysis that includes effect size, power and level of significance with references for how the sample size was determined. Explain the rate of attrition and possible number who fail the screening, with references as appropriate.]

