The number of subjects to be recruited for this study is approximately 150. Assuming 15% attrition, 127 participants will complete the study. With $\alpha=0.05$ and $N=127$, and assuming $SD=6.0\%$ (based 6-month weight loss in the online condition of our recent weight loss trial), we will have 80% power to detect mean 6-month weight change of $\pm 1.5\%$ or greater using a two-sided one-sample t-test.

Enrollment of UConn Students and/or Employees: [Will UConn students be enrolled? If so, describe if these students include those who any key research personnel teaches, or for whom any key research personnel has responsibility. Will UConn employees be enrolled? If so, describe if these employees report to any key personnel. For each group, explain why this population is *necessary* to the study. Tip: convenience is not sufficient justification.]

UConn students and employees may be enrolled if they meet eligibility requirements and are interested in completing the study. Students and employees directly reporting to key personnel on this project will be excluded from participation.

Enrollment of Key Personnel, Spouses or Dependents/Relatives: Will study key personnel, spouses of key personnel, or dependents/relatives of any key personnel be enrolled in the study? If so, describe and provide justification.

No.

For EACH Participant Population Describe Screening Procedures, if applicable: [Describe when participants will be screened and how this will occur. Include copies of all screening forms and related documents. Describe procedures to notify participants of the screening result, if applicable. Provide a copy of the screening instrument.]

We are recruiting overweight and obese individuals of all races and ethnicities, income, and education levels between the ages of 18 and 75 years in the United States. Participants must have regular home Wi-Fi connectivity.

Anticipated Study Time Frame: [Describe the estimated time frame of the study from anticipated start to anticipated finish. If the study will occur in more than phase include these in the time frame. Use of a table is often helpful.]

Project Time Frame:

This study will last for approximately 1 year and will include the following components:

Month	Nov	Dec	Jan	Feb	Mar	Apr	May	Jun	Jul	Aug	Sep	Oct
Start-up	X	X										
Recruitment			X	X	X							
Intervention					X	X	X	X	X	X	X	X
Follow-ups								X	X	X	X	X
Data manag	X	X	X	X	X	X	X	X	X	X	X	X

ement and analyse s											
Final Report											X

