Follow-ups are completed at 3-months and 6-months after the start of the intervention. Participants will receive an online follow-up survey during their 13th week and 27th week after the start of the intervention. This survey will be a repeat of some of the measures assessed at baseline (indicated in the measures table below) and questions to solicit participants' feedback on the weight loss program. We will also collect weight at the 3-month and 6-month mark.

WW Memberships:

Participants will be given a free WW membership for 6-months so they can access the WW app and virtual workshops. At the end of the study, memberships will end but they will be allowed to use the publicly available WW apps and programs with purchase.

Adverse Events:

Adverse events will be formally assessed at follow-ups by asking a question in the REDCap survey. If participants gain 5% or more weight during the intervention, this will be treated as an adverse event. The participant will receive a phone call from a UConn RC and they will be asked questions about what might be going on with their weight gain. We will also re-assess Binge Eating Disorder (BED) at this time. If BED is present, we will treat it as a study-related AE. We will only re-assess BED once after the telephone screening, even if there are multiple AE's for weight gain. Participants will not be removed from the intervention if they have 5% or more weight gain.

[Describe study procedures for use of interviews or focus groups if applicable. Include details such as how long each procedure will take to complete, who will be asked to participate in these procedures and where these procedures will be conducted. Provide copies of interview and focus group questions/topic areas.]

N/A

[If the study includes *measures, survey instruments and questionnaires (including the collection of demographic data)*, identify each and, if available, provide references for the measures. Describe what they intend to measure (relate to purpose/hypothesis) and their psychometric

properties (e.g., reliability and validity). Identify any that were specifically created for the study and attach a copy for IRB review.]

Data Collected	List of Measures	Screening	Baseline	During Intervention	3m F/up	6m F/up	Method
BMI	Height	X					REDCap
	Weight	X	X	X	X	X	Scale/REDCap
Demographics	Age, gender, income, employment, marital status, race/ethnicity, household composition*	X	X				REDCap

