Medical History	Assesses exclusionary medical conditions*	X	X				REDCap
Food Cravings	Food Craving Inventory ¹⁶		X		X	X	REDCap
Sleep Behavior	Pittsburgh Sleep Quality Index ¹⁷		X		X	X	REDCap
Quality of Life	Impact of Weight on Quality of Life-Lite ¹⁹		X		X	X	REDCap
Dietary Screener	The Five Factor Screener ³⁶		X		X	X	REDCap
Hunger	The Hunger Visual Analogue Scale ³⁷		X		X	X	REDCap
Self-Compassion	Self-Compassion Scale ³⁸		X		X	X	REDCap
Habits	Self-report Behavioral Automaticity Index ³⁹		X		X	X	REDCap
Physical Activity	Global Physical Activity Questionnaire (GPAQ) ²¹		X		X	X	REDCap
Wellbeing	The World Health Organization- Five Well-Being Index (WHO-5)		X		X	X	REDCap
Binge Eating Disorder	SCID Interview for BED ²³	X					Interview
Depression	Patient Health Questionnaire (PHQ-8) ²⁴		X				REDCap
Social Media Use	Social Media Use*		X				REDCap
History of WW Use	History of ever using WW in the past*				X		REDCap
WW App use	Data extraction			X	X	X	File transfer from WW
WW Virtual Workshops	Data extraction			X	X	X	File transfer from WW
Private Facebook group	Data extraction			X	X	X	Grytics
Intervention Feedback	Acceptability, satisfaction, burden*					X	REDCap

* Investigator-derived items

Psychometric properties for non-investigator derived measures:

Food Craving Inventory: The food craving inventory measures food craving through two subscales: subjective cravings and consumption of particular foods (White et al., 2012). The first subscale (subjective) assessed the frequency of subjective cravings for 47 different foods. The second subscale (behavioral) was intended to measure the extent to which participants gave in to craved foods.¹⁶

Pittsburgh Sleep Quality Index: The Cronbach's alpha is 0.83, demonstrating a good internal consistency (Smyth, 2012). It is noted that previous studies using different populations of older adults have reported high validity and reliability.²⁵

Impact of Weight on Quality of Life-Lite: The total score of all five subtype measures of the scale reported a high reliability of 0.96. In addition, IWQOL-Lite-CT Psychosocial scores correlated moderately to strongly with scores on the SF-36 MCS (0.49 at baseline; 0.41 at week 52).²⁷

The Five Factor Screener is a survey regarding how frequently someone consumes different food items. This screener has moderate validity suggesting that this screener can be useful to assess intake of various food items.³⁶

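### After screening, binge eating disorder is actively assessed only after a 5% weight gain and at most once, so any count of it will be incomplete

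*Protocol*

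**What the plan says.** BED is an exclusion criterion, checked by structured interview during the telephone screening (protocol, Exclusion Criteria). A case found later is therefore newly detected.

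The Adverse Events section sets the only later interview. The trigger is weight: "If participants gain 5% or more weight during the intervention, this will be treated as an adverse event". A coordinator then telephones the participant, and BED is re-assessed on that call. The section continues: "If BED is present, we will treat it as a study-related AE". It then sets a limit: "We will only re-assess BED once after the telephone screening", and this applies even when weight-gain events recur.

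In the measures table, the row for the "SCID Interview for BED" is marked at screening and at no later time point.

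All participants also get one adverse-event question in the follow-up surveys, which go out in weeks 13 and 27. Its wording is not given. Data Safety Monitoring refers to a separate adverse-event procedure for staff, which is not among the documents. Neither the protocol's Data Analysis section nor the SAP defines a BED rate, a denominator for one, or any safety analysis.

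**The concern.** Active detection of an event that the protocol says in advance it will treat as study-related is made to depend on another outcome, weight, and the intervention is designed to push weight the other way. The better the program works on weight, the fewer people are interviewed. BED that starts in someone who is losing weight, stable, or up by less than 5% is not actively looked for. Someone who is negative at a first gain is not interviewed again after a second.

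What is at stake is how a BED count would be read. A low number could mean that the condition was rare or that few people were asked, and the data would not separate the two. Those interviewed are also selected on weight gain, so a rate among them cannot be carried over to the whole sample.

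**Working it through.** **The plan's own figure.** Justification of Sample Size gives 15% attrition ("Assuming 15% attrition, 127 participants will complete the study"), SD 6.0%, two-sided alpha 0.05, and 80% power for a mean change of 1.5%. Enrolment is stated separately: "The total number of subjects that will be enrolled into the intervention will be 150".

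- Completers: 150 × 0.85 = 127.5, stated as 127.
- Noncentrality: (1.5 / 6.0) × √127 = 2.82, with 126 degrees of freedom.
- Power: 79.8% by the noncentral t, 80.4% by the normal approximation.

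The figure reproduces. It does not concern BED, but its SD ("based 6-month weight loss in the online condition of our recent weight loss trial") is the documents' only information on the spread of weight change, so it is used below.

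**Share of participants who reach the trigger.** Assumptions: percent change from baseline is normal with SD 6.0 and mean μ. The documents do not state an expected mean, so μ is set at 0, −1.5, −3 and −5.

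- (a) At month 6: 1 − Φ((5 − μ)/6).
- (b) At any time: (a) + exp(2 × 5 × μ / 36) × Φ((−5 − μ)/6). This is a Brownian path ending at mean μ and SD 6, watched continuously.

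| Mean change | (a) month 6 | of 150 | (b) any time | of 150 |
|---|---|---|---|---|
| 0 | 20.2% | 30 | 40.5% | 61 |
| −1.5% | 13.9% | 21 | 32.4% | 49 |
| −3% | 9.1% | 14 | 25.2% | 38 |
| −5% | 4.8% | 7 | 17.2% | 26 |

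Anyone above the threshold at month 6 has crossed it, so (a) is a floor for the trigger, which applies throughout the intervention. Column (b) is generous because weight is taken weekly, not continuously. A simulation of the same path in 24 weekly steps gave 26.7% at −1.5% and 13.0% at −5%, between the two columns.

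Never re-interviewed: from 100 − 40.5 = 59.5% to 100 − 4.8 = 95.2%. The upper end uses month 6 alone. On column (b) alone the range is 59.5% to 82.8%. It is a majority in every case.

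**Cases missed.** The documents give neither a BED incidence nor the chance of a 5% gain among those who develop BED. If a share g of new cases gains 5% or more, the interview can find at most g of them. For an assumed 6 new cases, g = 0.2 gives 6 × 0.2 = 1.2 and g = 0.5 gives 6 × 0.5 = 3. The yield is lower if BED starts after the single re-assessment. These values only illustrate and do not estimate the shortfall.

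**The denominator.** Take the same assumed 6 cases with g = 0.5, and 21 people interviewed (the month 6 figure at −1.5%). The true rate is 6/150 = 4.0%. The detected cases give 3/150 = 2.0% over all enrolled, but 3/21 = 14.3% over those interviewed. The first is too low and the second too high.

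**The case against.** The strongest defence is that triggered assessment is an openly stated choice in a one-arm, minimal-risk study of preliminary outcomes, in people already interviewed for BED at entry. No aim and no planned estimate depends on BED. That stands, and it limits the weight of this point. It does not close the gap in detection.

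Four stronger readings are tempting, and the documents do not support them.

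- A reader might infer that most participants can never be counted. The adverse-event question reaches every survey respondent, so BED could be self-reported, and the separate staff procedure might prompt for it. Nothing in the documents shows that either asks about binge eating.
- A reader might infer that the safety result understates BED. No such result is planned, so no stated figure is wrong. A count can fall short, but a rate among those interviewed could be too high for the sample.
- A reader might infer that the once-only limit contradicts the study-related label. How a detected event is classified and how often it is looked for are separate matters, and both rules can hold together.
- A reader might infer that BED is the one harm that the protocol attributes to the program. The risk sections name exercise injury, breach of confidentiality and discomfort with the measures or app, and not BED. The Adverse Events sentence is a classification rule for detected cases.

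It is also fair to say that the percentages count interviews not held, not cases missed, and that brief survey items would not diagnose BED as the structured interview does.

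**Conclusion.** The point holds as a gap in ascertainment. After screening, BED is actively assessed only in participants who gain 5% or more, and once at most. For the rest, detection depends on a general question of unknown wording. Under normally distributed change with the plan's SD of 6.0% and assumed mean losses of 0 to 5%, about 60% to 95% of participants would never be re-interviewed. That majority holds under every assumption tried, including the generous one of no mean loss and continuous monitoring.

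Any BED count is therefore incomplete, and a rate among those interviewed does not describe the whole sample. The number of missed cases cannot be computed from the documents. The primary weight analysis and its power are unaffected.

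**What to change.** Add one or two binge-eating screening items to the existing week 13 and week 27 REDCap surveys for all participants, worded identically at both. Report positives out of all respondents, separately from interview-confirmed BED. On the plan's attrition, up to 127 of 150 (84.7%) would be covered at 6 months, against about 5% to 40% reached by the triggered interview.

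Report any interview-based BED count with the number re-assessed, and state that re-assessment was triggered by weight gain. If the items cannot be added, this reporting line is the minimum.

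The cost is slightly longer surveys, some positive answers to handle under the existing adverse-event procedure, and items that are not equivalent to the SCID, so their count cannot be compared directly with the screening interview. No change to participants' care is proposed.

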Aim 1: We will summarize the use of each component, engagement in the online community and virtual workshops, and answers to questions assessing program acceptability. We will calculate percent weight change from baseline to 3 months and baseline to 6 months. For participants who do not provide weight at 6 months, we will use a baseline observation carried forward method (i.e., assume no weight loss). Secondarily, we will calculate a complete case 6-month weight change. For both the intent-to-treat and complete case estimates, we will use a one-

sample t-test to compare mean percent weight loss to the null hypothesis of no weight change (i.e., 0% weight loss). We will also describe the distribution of weight loss (e.g., median, IQR, range), and will calculate the proportion of participants who achieve clinically significant weight loss (i.e., $\geq 5\%$). We will assess changes in diet quality, physical activity, quality of life, external and internal eating, sleep quality, food cravings, and mood using the same approach as examining weight changes.

Aim 2: We will examine associations between total use of program components (and each individual program component) and change in weight, diet quality, moderate and greater intensity physical activity, mood, and quality of life using correlations and linear regression models.

Aim 3: We will examine associations between overall engagement in the virtual workshop ~~with percent weight loss at 3- and 6-months using correlations and linear regression models, and associations with $\geq 5\%$ weight loss with logistic regression models.~~

Inclusion/Exclusion Criteria: [List ALL inclusion and exclusion criteria. Any proposed exclusion criterion based on gender (women of childbearing potential), age, or race must include justification for the exclusion.]

Inclusion Criteria:

- 18-75 years old
- BMI 25-45 kg/m²
- Has Wi-Fi connectivity at home
- Able to participate in the study in English
- Self-reported desire to lose weight
- Willing to follow recommendations required by study protocol
- Willing to include demographic information (e.g., ethnicity, income and education)
- Lives in the United States

Age justification: Children under 18 require different programming for weight loss and maintenance given their developmental needs. Weight loss is often not indicated for elderly adults and should be medically supervised.

Exclusion Criteria:

- Pregnant, lactating, or plans to become pregnant during study period
- Bipolar disorder, substance abuse, psychosis, bulimia, binge eating disorder, or severe depression. Binge eating disorder will be assessed using a structured clinical interview during the telephone screening. All other mental health, including other eating disorders, is assessed using a self-report question on the initial screening survey. We will rely on self-report in place of formally assessing all mental health disorders.
- Had bariatric surgery or plans to have any surgery during the study
- Unable to make dietary changes or increase physical activity
- Unable to walk $\frac{1}{4}$ mile unaided without stopping
- Smoker or use nicotine vape daily

- Participants that are currently, or within the last 6 months, trying to lose weight via a structured weight-loss program (e.g., at a medical center, university, commercial programs)
- Participants who were a member of WW within the past 12 months
- Participants who are involved in any other research studies at this time
- **Weight loss of ≥ 5 kg in the previous 6 months**
- Reported health problems that make weight loss or unsupervised exercise unsafe or unreasonable (e.g., chronic pain, orthopedic limitations, heart problems)
- Untreated thyroid disease or any changes (type or dose) in thyroid medication in last 6 months
- Taking any prescription medication with known effects on appetite or weight (e.g., oral steroids, weight loss medications such as Qsymia, Contrave, etc.) with the exception of subjects on a stable dose of SSRIs for 6 months
- Chronic/inflammatory gastrointestinal disorders (irritable bowel syndrome is acceptable)
- History of heart problems (e.g., angina, bypass surgery, myocardial infarction, etc.) within previous 6 months
- Diagnosis of type 1 or type 2 diabetes
- Major surgery within the previous 6 months
- Presence of implanted cardiac defibrillator or pacemaker
- History of cancer within past 5 years or current treatment for cancer (completely resected basal or squamous cell carcinoma acceptable if treatment completed more than 6 months prior to enrollment)
- Meets criteria for severe depression on the PHQ-9 (score of >20)
- Hospitalization for psychiatric disorders during the past 12 months
- Not willing to sign an NDA; or indicated they do not want to agree to NDA's terms
- Unable to attend any virtual workshop meeting times
- Does not have an iPhone

[Describe the conditions under which participants may be removed from the study, i.e., noncompliance with study rules, study termination, etc.]

Participants will be withdrawn from the study if: they drop from participation, do not complete all screening procedures or post inappropriate content on the social network. Participants reporting that they would like to withdraw from the study will be given the option to: 1) withdraw from all intervention-related activity and contacts, but still complete the final assessment or 2) withdraw from the study completely with no additional study contact. If a participant becomes pregnant during the study, they will be withdrawn from the intervention, but will be given the option to still complete the follow-up assessments.

Potential Harms/Risks and Inconveniences: [Describe the potential risks to participants (and secondary participants, if applicable) and *steps taken to minimize risks* for each participant population. Assess the likelihood of the risk occurring and, if it were to occur, the seriousness to the participant. Types of risks to consider include, but are not limited to: physical, psychological, social, legal, employment, and financial.]

Possible risks for being in this study includes: Injury while exercising, breach of confidential information, and discomfort completing measures. The attempt to avoid risks to participants will be addressed by: suggesting moderate intensity exercise to avoid discomfort, pain, or injury. Participants reporting discomfort will be referred to their PCP. Injuries are unlikely to occur since we screen out medical conditions that could make someone prone to injury and we only suggest moderate activity. Moderate-level physical activity is 3.0 - <6.0 METs, which includes activities such as walking briskly (2.5 to 4 mph), playing doubles tennis, or raking. We also provide

participants with information on exertion level and remind them to seek medical attention if there is pain. Tracking data will be stored electronically in REDCap, a network secure data entry program; any data on paper will be stored in a locked file cabinet; and participants will be informed that they may withdraw from the study at any time if they feel discomfort with any of the study procedures.

Participant engagement data (i.e., WW app, Virtual Workshops, weight data) will be continuously collected by WW. Facebook engagement data will be collected through Grytics that study staff have access to through a secure login. The WW investigator will transfer these files via a UConn OneDrive folder which only [name] and [name] access. [name] or [name] will save the data to the UConn research drive and delete it from the OneDrive. WW will review by assigning a staff member to read and assess each interaction in the Facebook group on a regular basis. We will also assess for large weight changes to ensure only the participant is using the app. Any privacy-related problems will be brought to the attention of the PI immediately.

[Describe any anticipated inconveniences the participants may experience (such as: their time, abstention from food, etc.).]

Participants will be asked to dedicate up to 33 hours of their time over the course of 7 months to participate in this study.

Instances of threats or harassment in the Facebook group will be handled in the manner below:

Profanity & Vulgarity

- R-rated language
 - Remove all R-rated language used as a form of a personal attack, e.g. "You are a b****" or "F*** you". These specific words are not permitted at all times: "c***", "d***", "c**k", "b*** f***", "m****f*****".
- "Shit"
 - Permit content that contains the word "shit" and all of its variants, unless used in the form of a personal attack, e.g., "You don't know shit."
- "Ass", "Crap", "Bullcrap", "Hell", & "Damn"
 - Permit these words and their variants - kick ass, bad ass, pain in the ass, etc., unless used in the form of a personal attack, e.g., "I'm going to kick YOUR ass."
- Pornographic content & Sexually graphic or explicit language
 - Remove all pornographic content as well as sexually graphic or explicit language. Apply the standard of PG-13 TV. For example, it is ok for fans to say, "WW has helped me look sexier than ever!" However, it is not ok for fans to describe sexual acts in detail.
- Camouflaged spellings, e.g., "f*ck" or "p0rn"
 - Moderate words with transparently camouflaged spellings as you would their obvious stand-ins, e.g., "f*ck" is permitted, as long as it is NOT used as a personal attack.
- Acronyms
 - Permit acronyms with widespread cultural acceptance, e.g., "WTF" or "LMFAO".

Personal Attacks

- Remove all content that includes personal attacks. This includes disrespecting, insulting, or attacking users or posts in an aggressive manner. For example:
 - Calling other users losers, idiots, morons, etc., are all considered personal attacks.
 - Lewd, suggesting, crude, or cruel comments directed toward other users should also be removed.

- This can refer to either a specific individual or a group of people (e.g. "You idiots on this thread need to shut up")
- Permit friendly banter using your own discretion.
- Remove all content that may result in others feeling threatened, specifically targeted, or abused.
- Remove all content inciting or directly referring to violence, past violence, or the threat of violence.

Trolling

- A troll is "someone who posts inflammatory, extraneous, or off-topic messages with the primary intent of provoking readers into an emotional response or disrupting normal on-topic discussion."
- Individual trolling posts may not violate any one particular guideline.
- It will be up to the Senior Resolution Specialist to identify trolling attempts and take appropriate action (removal, banning).

Discrimination, Religious, and Political Themes

- Remove all content that advocates or condones discrimination or prejudice based upon race, color, religion, creed, sex, sexual orientation, national origin, age, disability, or veteran status.
- Remove all content that advocates religion or religious themes or imagery. An author mentioning religion would not typically be offensive to others and is acceptable. However, an author advocating or pushing religion, or criticizing another's lack of, is NOT acceptable.
- Remove all content that provokes and calls on a specific action in response to a political and/or current event. If the content clearly states how these political issues relate to their wellness journey, do not remove/hide post. All political posts should be downtrended.

Benefits: [Describe anticipated benefits to the individual participants. If test results will be provided, describe and explain procedures to help participants understand the results. If individual participants may not benefit directly, state so here. Do not include compensation or earned course credits in this section.]

Participants may or may not benefit from participating in the study. Benefits that could occur are losing weight through the exercise and lifestyle changes. Through interacting with other participants and the coach during the virtual workshops, participants may also feel supported in their behavioral change efforts.

[Describe anticipated benefits to society (i.e., added knowledge to the field of study) or a specific class of individuals (i.e., athletes or autistic children).]

Societal benefits include providing evidence to support intervention delivery modalities that are more conducive to modern lifestyle (i.e., more virtual options).

Risk/Benefit Analysis: [Describe the ratio of risks to benefits. Risks to research participants should be justified by the anticipated benefits to the participants or society. Provide your assessment of anticipated risks to participants and steps taken to minimize these risks, balanced against anticipated benefits to the individual or to society.]

The possible risks of the study (including injury during exercise, psychological discomfort while completing surveys or using the WW app, and breach of confidentiality) are minimal and are outweighed by the possible benefits to participants (weight loss).

Economic Considerations: [Describe any costs to the participants or amount and method of compensation provided. Describe how you arrived at the amount and the plan for compensation; if it will be prorated, please provide the breakdown. Experimental or extra course credit should be considered an economic consideration and included in this section. Indicate when participants will receive compensation.]

Economic burden to subjects includes the time needed for screening and study participation. There is no cost to participants for participating in the study. Depending on smartphone data usage plan for each participant, usage charges may incur due to increased use of mobile apps.

Participants will be paid in the form of online Amazon gift cards. Participants will receive \$20 compensation for completing the baseline visit, \$50 for completing the 3-month survey, and \$50 for completing the 6-month survey. Additionally participants will be allowed to keep the study scale.

Participants who complete the Qualtrics initial screening survey, whether or not they participate in this study, will receive Qualtrics incentives. Their incentives are based on a points system. Respondents accumulate points as they take surveys and then trade in points for E-gift cards to anywhere of their choice (amazon, walmart, target, etc.). The compensation Qualtrics provides is separate from the compensation for participating in the baseline and follow-ups of this trial.

Data Safety Monitoring: [This is a prospective plan set up by the study investigators to assure that adverse events occurring during studies are identified, evaluated, and communicated to the IRB in a timely manner. Although the investigators initially propose a Data Safety Monitoring Plan (DSMP), the IRB must approve the plan and may require revision of the plan. A DSMP is required for all human studies at the University of Connecticut except for studies reviewed under the Exempt Criteria. For studies that present more than minimal risk to participants, the IRB will review and determine on a case-by-case basis whether a data safety monitoring board is most appropriate. Please refer to the IRB's policy regarding data safety monitoring *before* completing this section - <http://research.uconn.edu/policies-procedures>.

Issues that should be addressed in the DSMP include the following:

1. Frequency of the monitoring.
2. Who will conduct the monitoring (Under UConn policy a student cannot be the sole person responsible for monitoring the data and safety of the protocol procedures?)
3. What data will be monitored (include compliance with approved IRB protocol?)
4. How the data will be evaluated for problems?
5. What actions will be taken upon the occurrence of specific events or end points?
6. Who will communicate to the IRB and how will communication will occur?
7. Describe procedures to inform the sponsor.

Sample response to issues listed above for minimal risk/ slight increase over minimal risk – “Survey results will be monitored by the PI in conjunction with the student investigator once every two weeks (items 1, 2 and 3). Survey responses will be reviewed to monitor for clarity (i.e., the same question is

skipped by 5 or more participants). In that case, the question will be revised and an amendment will be submitted to the IRB (items 4, 5 and 6)."

Since this study is minimal risk we will not have a safety board. Data will be monitored by the data manager weekly and at the end of each assessment phase. Data from tracking forms and surveys, and engagement data received from WW will be cleaned and assessed for missingness. A full report will be generated at 6-months for PI and WW review. The report will be submitted to the IRB at the closing of the project.

Adverse events will be assessed at follow-ups UConn staff will follow an AE protocol, which will include instructions on what is considered an adverse event and what steps are needed to be taken.

Privacy/Confidentiality Part 1: [Explain how the privacy interests of participants will be maintained during the study (note that **privacy pertains to the individual not to the data**). Describe how data will be coded. Do not use the any potentially identifiable information such as initials of participants as part of the code. Explain how long data will be kept in an identifiable format and how long de-identified data will be retained. Explain how long the master key or audio or video recordings obtained, will be kept. Consider whether keeping de-identified data will be retained indefinitely and whether participants may be contacted for a follow-up study (explain procedures to retain identifiable contact data is kept.)]

REDCap will be used for data entry and management. The database will be maintained on UConn servers where security will be maintained through access controls. Files will be managed by the data manager and project coordinators, who will control user access and rights. For each user, REDCap will require a REDCap profile, username and password to enter the program. Staff will only have access to the database if the data manager has given them access. UConn IRB and their representatives, and study personnel will have access to the research data, as will the study sponsor if requested. All participants will be assigned an ID number, which will link them to their study data. The ID number will be 3-4 numerical characters representing the number of participants in the study. PHI fields will be stored in a separate REDCap form from other data collection forms. Data will be completely de-identified once the last assessment is complete and cleaned the data and assess for any missingness or errors. At this time the link between ID number and study data will be destroyed. Study data in the form of hard copies will be stored in a locked file cabinet managed by the program director and will be destroyed 5 years after completion of the study.

WW scales will be used to collect weight from participants. The scale will be mailed directly from WW to the participant.

Participant information entered into the WW app and any data from the virtual workshops will be transmitted from the WW investigator to the Research Coordinators [name] and [name] using a UConn OneDrive folder that only [name] and [name] (and WW) will be given access to. Records will contain the WW membership ID number, which UConn can use to link to study ID. Only UConn will hold the master key to the assessment data and study ID numbers. Only data relevant to participants in this study will be given to UConn investigators.

If identifiable, sensitive information (illegal drug use, criminal activity, etc.) will be collected, state whether a Certificate of Confidentiality will be obtained.

N/A

Be sure to state whether any limits to confidentiality exist (e.g. mandated reporting) and identify any external agencies (study sponsor, FDA, etc.) that will have access to the data.

